9.3 Primary Efficacy Endpoints and Analyses

9.3.1 Primary Efficacy Endpoints

The co-primary endpoints of this study in Period A are:

- Achievement of PASI 90 at Week 16, among subjects in the ITT_A Population.
- Achievement of sPGA 0 or 1 with at least 2-grade improvement from Baseline at Week 16, among subjects in the ITT_A Population.

The primary endpoint of this study in Period B is:

- Achievement of PASI 90 at Week 52, among subjects in the ITT_B_NR Population.

9.3.2 Main Analysis of Primary Efficacy Endpoints

The primary efficacy endpoints will be analyzed as specified in Section [9.1](#).

The attributes of the estimands corresponding to the primary efficacy endpoints in Period A and Period B are summarized in [Table 1](#).

Table 1. Summary of the Estimand Attributes of the Primary Efficacy Endpoints

Estimand Label	Attributes of the Estimands				
	Treatment	Endpoint	Population	Handling of Intercurrent Events	Statistical Summary
PASI 90 at Week 16	RZB and APR	PASI 90 at Week 16	ITT_A	
 Subjects who receive alternative PsO treatment regardless of premature discontinuation of study drug before Week 16 will be considered as non-responders 	Difference in the percentage of subjects achieving PASI 90 at Week 16 in RZB group in comparison with APR group
sPGA 0/1 at Week 16		sPGA 0/1 with at least 2-grade improvement from Baseline at Week 16			Difference in the percentage of subjects achieving sPGA 0/1 with at least 2-grade improvement from Baseline at Week 16 in RZB group in comparison with APR group
PASI 90 at Week 52	APR/RZB and APR/APR	PASI 90 at Week 52	ITT_B_NR	
 Subjects who receive alternative PsO treatment regardless of premature discontinuation of study drug before Week 52 will be considered as non-responders Subjects who satisfy rescue criteria or receive the rescue medication at Week 28 or Week 40 will be considered as non-responders 	Difference in the percentage of subjects achieving PASI 90 at Week 52 in APR/RZB group in comparison with APR/APR group

9.3.3 Sensitivity and Supplementary Analyses of the Primary Efficacy Endpoints

There will be no sensitivity analysis for the primary efficacy endpoints.

9.4 Secondary Efficacy Endpoints and Analyses

9.4.1 Key Secondary Efficacy Endpoints

The ranked secondary endpoints are as defined in Section [3.2](#).

9.4.2 Main Analyses of Key Secondary Efficacy Endpoints

The secondary efficacy endpoints will be analyzed as specified in Section [9.1](#).

The attributes of the estimands corresponding to the key secondary efficacy endpoints are summarized in [Table 2](#).

Table 2. Summary of the Estimand Attributes of the Key Secondary Efficacy Endpoints

Estimand Label	Attributes of the Estimands				
	Treatment	Endpoint	Population	Handling of Intercurrent Events	Statistical Summary
PASI 75 response at Week 16	RZB and APR	PASI 75 response at Week 16	ITT_A	
 Subjects who receive alternative PsO treatment regardless of premature discontinuation of study drug before Week 16 will be considered as non-responders 	Difference in the percentage of subjects achieving PASI 75 response at Week 16 in RZB group in comparison with APR group
PASI 75 at Week 52	APR/RZB and APR/APR	PASI 75 response at Week 16	ITT_B_NR	
 Subjects who receive alternative PsO treatment regardless of premature discontinuation of study drug before Week 52 will be considered as non-responders Subjects who satisfy rescue criteria or receive the rescue medication at Week 28 or Week 40 will be considered as non-responders 	Difference in the percentage of subjects achieving PASI 75 at Week 52 in APR/RZB group in comparison with APR/APR group
sPGA 0/1 at Week 52		sPGA 0/1 with at least 2-grade improvement from Baseline at Week 52			Difference in the percentage of subjects achieving sPGA 0/1 with at least 2-grade improvement from Baseline at Week 52 in APR/RZB group in comparison with APR/APR group

9.4.3 Sensitivity and Supplementary Analyses for Key Secondary Efficacy Endpoints

There will be no sensitivity analysis for the ranked secondary efficacy endpoints.

9.5 Additional Efficacy Analyses

All additional efficacy endpoints will be analyzed as specified in Section 9.1.

Period A: Additional efficacy endpoints will be compared between the RZB and APR treatment groups among the ITT_A Population at each visit.

Period B: Additional efficacy endpoints will be compared between the APR/RZB and APR/APR treatment groups among the ITT_B_NR and ITT_B_Combined Populations, and between the RZB/RZB and APR/APR treatment groups among the ITT_LT Population, at each visit in Period B.

Additional efficacy endpoints will also be summarized by the APR/RZB and APR/APR treatment groups among the ITT_B_R Population at each visit in Period B.

During the Period of Rescue RZB: Additional efficacy endpoints will be summarized among the ITT_Res Population at each visit after the use of Rescue RZB.

9.6 Efficacy Subgroup Analyses

Subgroup analysis will be performed on co-primary endpoints in Period A based on the following subgroups, among the ITT_A Population:

- Age group: < 40, ≥ 40 to < 65, ≥ 65
- Sex (male, female)
- Race (white, non-white)
- Smoking (current, ex or never)
- Body mass index (normal: < 25, overweight: ≥ 25 to < 30, obese: ≥ 30)
- Baseline PASI score (by median)
- Psoriatic arthritis (yes, no)

- Prior systemic (including biologic) treatment ($0, \geq 1$)

Age ≥ 65 years or BMI ≥ 30 subgroups will be combined with their adjacent subgroup when having fewer than 10% subjects.

10.0 Safety Analyses

10.1 General Considerations

Safety data will be summarized among the Safety_A, Safety_B_R, Safety_B_NR, and Safety_LT Populations. Safety summaries will be presented by treatment group. For the safety analysis, subjects are analyzed based on the treatment actually received, determined by the first dose of study drug that the subject received during the specific analysis period.

The overview of TEAEs, and potentially clinically important (PCI) findings in laboratory variables and vital sign variables will also be summarized among the Safety_B_Combined, Safety_Res, and ALL_RZB Populations.

Missing safety data will not be imputed.

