2.3 Treatment Assignment and Blinding

All subjects will be assigned a unique identification number by the IRT at the screening visit. For subjects who rescreen, the screening number assigned by the IRT at the initial screening visit should be used. The IRT will assign a randomization number that will encode the subject's treatment group assignment according to the randomization schedule.

In Period A (Baseline to Week 16), subjects will be centrally randomized to risankizumab (Arm 1) or apremilast (Arm 2) in a 1:2 ratio at Baseline. Randomization will be stratified

by Baseline body weight (≤ 100 kg, > 100 kg) and prior exposure to any systemic and/or biologic treatment for Po ($0, \geq 1$).

In Period B (Week 16 to Week 52), subjects initially randomized to risankizumab (Arm 1) will continue to receive risankizumab. Subjects initially randomized to apremilast (Arm 2) will be centrally re-randomized at the Week 16 visit in a 1:1 ratio to receive either risankizumab (Arm 2a) or apremilast (Arm 2b). Re-randomization will be stratified by PASI 75 response (responder, non-responder) at Week 16. Rescue risankizumab will be offered to subjects who are re-randomized to apremilast (Arm 2b) and are PASI 50 non-responders at Week 28 (Arm 3a) or Week 40 (Arm 3b).

This is an open-label study; however, the efficacy assessor will remain blinded to each subject's treatment, clinical laboratory results, and all subject safety data during the course of the study.

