10.2.1 Treatment-Emergent Adverse Events

A treatment-emergent adverse event (TEAE) in each analysis period is defined as follows:

A TEAE in Period A is defined as any AE with an onset date on or after the first dose of study drug in Period A, and

- Within the minimum of (i) 140 days after the last dose of RZB in Period A and (ii) the first dose date of study drug in Period B for subjects who receive RZB at Baseline.
- Within the minimum of (i) 28 days after the last dose of APR in Period A and (ii) the first dose date of study drug in Period B for subjects who receive APR at Baseline.

A TEAE in Period B is defined as any AE with an onset date on or after the first dose of study drug in Period B and

- Within 140 days after the last dose of RZB in Period B for subjects who receive RZB in Period B.
- Within the minimum of (i) 28 days after the last dose of APR in Period B and (ii) the first dose date of rescue risankizumab (if any) for subjects who receive APR in Period B.

A TEAE during the administration of rescue risankizumab is defined as any AE with an onset date on or after the first dose of rescue risankizumab and within 140 days after the last dose of rescue risankizumab.

A TEAE during the administration of risankizumab (i.e., among the ALL_RZB Population) is defined as any AE with an onset date on or after the first dose of risankizumab and within 140 days after the last dose of risankizumab.

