10.3 Analysis of Laboratory Data

Data collected from central and local laboratories, including additional laboratory testing due to an SAE, will be used in all analyses, except for Baseline where SAE-related laboratory assessments on or before the first dose of study drug will be excluded. The clinical laboratory tests defined in the protocol operations manual (e.g., hematology and clinical chemistry) will be summarized.

Mean change from Baseline to each applicable post-baseline visit will be summarized for selected laboratory variables among the Safety_A, Safety_B_R, Safety_B_NR, and Safety_LT Populations. The following descriptive statistics will be presented by treatment groups: number of observations, Baseline mean, visit mean, mean change from Baseline and its standard error, and the 95% confidence interval of the mean change from Baseline.

In addition, laboratory parameters will be tabulated using shift tables from Baseline to minimum and maximum values among Safety_A, Safety_B_R and Safety_B_NR, and Safety_LT Populations categorized by the toxicity grade according to NCI CTCAE Version 4.03¹ of the laboratory used for each sample. A similar shift table will also be provided to summarize shifts from Baseline to the final post-baseline value in each period.

Laboratory abnormalities meeting CTC criteria grade 3 and 4 will be summarized among all safety populations.

Laboratory abnormalities will be evaluated based on Potentially Clinically Important (PCI) criteria ([Appendix C](#)). For each laboratory PCI criterion, the number and percentage of subjects who have a laboratory value meeting the criteria will be summarized. Listings will be provided to summarize subject-level laboratory data for subjects meeting PCI criteria.

In addition, the frequencies and percentages of subjects with post baseline liver specific function test values in ALT/SGPT, AST/SGOT, alkaline phosphatase, and total bilirubin will be categorized as follows:

- ALT > 3.0 × ULN
- ALT > 5.0 × ULN
- ALT > 10.0 × ULN
- ALT > 20.0 × ULN
- AST > 3.0 × ULN
- AST > 5.0 × ULN
- AST > 10.0 × ULN
- AST > 20.0 × ULN
- Alkaline phosphatase > 1.5 × ULN
- Total bilirubin > 1.5 × ULN
- Total bilirubin > 2.0 × ULN
- ALT and/or AST > 3× ULN and Total bilirubin > 1.5× ULN
- ALT and/or AST > 3× ULN and Total bilirubin > 2× ULN
- ALT > 3× ULN and Total bilirubin > 1.5× ULN
- ALT > 3× ULN and Total bilirubin > 2× ULN

The listing will include all subjects who met any of the following four criteria:

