10.4 Analysis of Vital Signs

Vital sign measurements of systolic and diastolic blood pressure will be summarized.

Change from baseline to each applicable post-baseline visit will be summarized for each vital sign variable among the Safety_A, Safety_B_R, Safety_B_NR, and Safety_LT Populations. The following descriptive statistics will be presented by treatment groups: number of observations, Baseline mean, visit mean, mean change from Baseline and its standard error, and the 95% confidence interval of the mean change from Baseline.

Vital sign variables will be evaluated based on potentially clinically important (PCI) criteria ([Appendix C](#)) among all safety populations. For each vital sign PCI criterion, the number and percentage of subjects who have a vital sign value meeting the criteria at least once in each period will be summarized. Listings will be provided to summarize subject-level vital sign data for subjects meeting PCI criteria.

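### SAP 10.3 and 10.4 give no rescue cut-off for laboratory and blood-pressure data, so under the first-dose rule post-rescue risankizumab values are counted under APR/APR in the Period B safety tables

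*SAP*

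**What the plan says.** SAP 10.1 gives the grouping rule for the safety tables, applied within each period: "subjects are analyzed based on the treatment actually received, determined by the first dose of study drug that the subject received during the specific analysis". Protocol 7.5 has the same rule, with the first dose counted from randomization or re-randomization.

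SAP 2.3 sets the limits of Period B: "In Period B (Week 16 to Week 52), subjects initially randomized to risankizumab (Arm 1) will continue to receive risankizumab". Within those weeks, risankizumab is offered to subjects re-randomized to apremilast who "are PASI 50 non-responders at Week 28 (Arm 3a) or Week 40 (Arm 3b").

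For adverse events, SAP 10.2.1 ends the apremilast window at rescue: "Within the minimum of (i) 28 days after the last dose of APR in Period B and (ii) the first dose date of rescue risankizumab".

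For laboratory data, SAP 10.3 plans mean changes at each applicable visit and shifts to the minimum and maximum. It adds: "A similar shift table will also be provided to summarize shifts from Baseline to the final post-baseline value in each period". It also plans grade 3-4, PCI and liver-category summaries. For blood pressure, SAP 10.4 plans mean changes by visit and PCI counts: "the number and percentage of subjects who have a vital sign value meeting the criteria at least once in each period will be summarized". Neither section mentions rescue.

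**The concern.** The safety of switching to risankizumab versus staying on apremilast is part of the stated objective (SAP 2.1). Only the apremilast arm can be rescued, so any misassignment runs one way: values measured on risankizumab enter the apremilast column. If the drugs differ on a parameter, the APR/APR mean moves toward risankizumab. A post-rescue abnormality may also be charged to apremilast.

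The tables would not match one another either. The APR/APR adverse-event table would stop at rescue, while the laboratory and blood-pressure tables under the same label would run to Week 52.

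**Working it through.** **1. Where the SAP ends APR/APR at rescue**

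| Summary | Treatment of post-rescue data | Place |
|---|---|---|
| TEAEs | cut at first rescue dose | SAP 10.2.1 |
| Treatment duration | cut at start of rescue | SAP 6.0 |
| Tablet compliance | planned tablets counted only before rescue | SAP 6.0 |
| Patient-years | cut at first rescue dose | SAP 10.2.4 |
| MMRM, continuous efficacy | post-rescue values excluded | SAP 9.2.2 |
| Laboratory | nothing stated | SAP 10.3 |
| Blood pressure | nothing stated | SAP 10.4 |

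**2. Which tables are affected**

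- Mean-change tables (laboratory and blood pressure) and laboratory shift tables are planned for Safety_B_NR, Safety_B_R and Safety_LT in Period B. Neither has a Safety_Res or ALL_RZB version, so post-rescue values there are misattributed but not counted twice.
- PCI findings are also summarized in Safety_B_Combined, Safety_Res and ALL_RZB (SAP 10.1), and grade 3-4 abnormalities in all safety populations (SAP 10.3). A post-rescue finding can then appear under APR/APR and again under risankizumab.
- Liver categories have no population of their own in SAP 10.3. The general rule in 10.1 applies.

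**3. Post-rescue visits per rescued subject**

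Visits come from Protocol Appendix D, after the Week 16 visit. Values at the rescue visit itself are taken as pre-dose (an assumption).

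| Data | Visits (week) | Rescue at Week 28 | Rescue at Week 40 |
|---|---|---|---|
| Chemistry | 20, 32, 44, 52 | 3 of 4 | 2 of 4 |
| CBC | 32, 52 | 2 of 2 | 1 of 2 |
| Blood pressure | 20, 28, 32, 40, 44, 52 | 4 of 6 | 2 of 6 |

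Appendix D excludes electrolytes and lipids at Weeks 20, 32 and 44. Their only scheduled value after Week 16 is Week 52, which is post-rescue for every rescued subject.

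**4. Share of APR/APR data**

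The plan has 60 APR/APR non-responders (SAP 2.4). That size reproduces the plan's stated power of more than 90%. With 50% versus 20%, the pooled chi-square gives Φ[(0.30·√60 − 1.96·√(2·0.35·0.65)) / √(0.25 + 0.16)] = Φ(1.56) = 94.1%. The present point does not touch that figure.

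The documents give no rescue rate. Let f be the rescued fraction and s the share of rescues at Week 28. Without dropout, the post-rescue share of records is f × [s·a28 + (1 − s)·a40], where a28 and a40 are the fractions in step 3. With f assumed at 10% to 50% (6 to 30 of 60) and s from 0 to 1:

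- Chemistry: 0.10 × 2/4 = 5% to 0.50 × 3/4 = 37.5%.
- CBC: 0.10 × 1/2 = 5% to 0.50 × 2/2 = 50%.
- Blood pressure: 0.10 × 2/6 = 3.3% to 0.50 × 4/6 = 33.3%.
- Any Week 52 value: share = f, so 10% to 50%.

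**5. Effect on a Week 52 mean difference**

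Let A be the mean change on apremilast (taken as the same for rescued and unrescued subjects had they stayed on it), R the mean on risankizumab and R* the mean in rescued subjects. The APR/APR mean is (1 − f)A + fR*. If R* = R, the difference from risankizumab is (1 − f)(A − R), a shrinkage by the fraction f. If R* = A, there is no shrinkage. If A = R = R*, there is nothing to dilute.

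**The case against.** The strongest reply is that rescue is its own analysis period. SAP 10.2.1 gives rescue a separate window in a list introduced as covering each analysis period, SAP 6.0 lists rescue risankizumab beside Periods A and B, and SAP 9.5 speaks of a rescue period. On that reading the first dose in the rescue period is risankizumab, and the period wording in 10.3 and 10.4 already separates the data.

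This makes the text less than certain, but it does not close the gap. Protocol 7.5 counts the first dose from randomization or re-randomization, and rescue is neither. If rescue ended Period B by itself, the explicit rescue clause in 10.2.1 would be unnecessary. And because mean-change and shift tables have no Safety_Res version, the alternative reading would leave post-rescue values in none of them.

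Other parts of the reply stand. The summaries are descriptive, with no between-group test. PCI and grade 3-4 findings after rescue also appear under risankizumab, and PCI findings are listed by subject, so they would not be hidden. TEAEs, exposure and efficacy are unaffected.

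A reader might infer that the SAP expressly keeps post-rescue values under APR/APR, or that the safety comparison as a whole is diluted by a known amount. The documents support neither. Sections 10.3 and 10.4 are silent, no rescue rate is given, and no laboratory or blood-pressure difference between the drugs is stated.

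**Conclusion.** The gap is real and should be closed. By the first-dose rule as written, laboratory and blood-pressure values after rescue fall under APR/APR in the Period B tables, against the SAP's own practice for the other data types in step 1.

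The visit counts per rescued subject follow directly from the schedule, given pre-dose measurement at the rescue visit. The share of APR/APR data does not. At Week 52 it equals the rescue rate, and 10% to 50% of 60 is only an illustration. In Safety_LT the APR/APR group also holds PASI 75 responders, so the same number of rescued subjects would be a smaller share there.

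Shrinkage by the full rescue fraction further requires that the drugs differ on the parameter and that rescued subjects, including those first dosed at Week 40, have reached the risankizumab mean by Week 52. It applies to means, not to minimum, maximum or PCI counts. Double counting is limited to summaries that also have a Safety_Res or ALL_RZB version.

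**What to change.** State in SAP 10.1, 10.3 and 10.4 that, for APR/APR in Period B, laboratory and vital-sign values are used only up to and including the last value on or before the first rescue risankizumab dose, keeping same-day pre-dose values. Derive minimum, maximum, final and ever-met results from those values only. Assign later values to Safety_Res and ALL_RZB, and define the analysis period for these data.

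Add Safety_Res mean-change tables and laboratory shift tables. Without them, the cut-off would remove post-rescue values from those summaries altogether.

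The cost is a few sentences, a date filter on a date the SAP already uses, and a few more descriptive tables. APR/APR will have fewer values at Weeks 32 to 52, so the number contributing at each visit should be shown.

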10.2 Adverse Events

Adverse events (AEs) will be summarized and presented using primary MedDRA System Organ Classes (SOCs) and preferred terms (PTs) according to the version of the MedDRA coding dictionary used for the study at the time of database lock. The actual version of the MedDRA coding dictionary used will be noted in the AE tables and in the clinical study report. When summarizing the number and percentages of subjects, subjects with multiple occurrences of the same adverse event will be counted once, and only the maximum severity level will be presented in the severity summaries, and the worst/highest relationship level in the relationship summaries.

10.2.1 Treatment-Emergent Adverse Events

A treatment-emergent adverse event (TEAE) in each analysis period is defined as follows:

A TEAE in Period A is defined as any AE with an onset date on or after the first dose of study drug in Period A, and

- Within the minimum of (i) 140 days after the last dose of RZB in Period A and (ii) the first dose date of study drug in Period B for subjects who receive RZB at Baseline.
- Within the minimum of (i) 28 days after the last dose of APR in Period A and (ii) the first dose date of study drug in Period B for subjects who receive APR at Baseline.

A TEAE in Period B is defined as any AE with an onset date on or after the first dose of study drug in Period B and

- Within 140 days after the last dose of RZB in Period B for subjects who receive RZB in Period B.
- Within the minimum of (i) 28 days after the last dose of APR in Period B and (ii) the first dose date of rescue risankizumab (if any) for subjects who receive APR in Period B.

A TEAE during the administration of rescue risankizumab is defined as any AE with an onset date on or after the first dose of rescue risankizumab and within 140 days after the last dose of rescue risankizumab.

A TEAE during the administration of risankizumab (i.e., among the ALL_RZB Population) is defined as any AE with an onset date on or after the first dose of risankizumab and within 140 days after the last dose of risankizumab.

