## 3 OBJECTIVES AND ENDPOINTS

### 3.1 Objectives, Hypotheses, and Estimands

---

The objective of the study is to evaluate the efficacy and safety of risankizumab versus apremilast for the treatment of adult subjects with moderate plaque PsO who are candidates for systemic therapy.

In addition, the study aims to evaluate the efficacy and safety of switching to risankizumab versus continuing on apremilast for subjects with moderate plaque PsO who do not achieve PASI 75 after 16 weeks of treatment with apremilast.

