- Period B (Week 16 to Week 52): Subjects initially randomized to risankizumab (Arm 1) will continue to receive risankizumab 150 mg as a single SC injection at Weeks 16, 28, and 40. Subjects initially randomized to apremilast (Arm 2) will be re-randomized at the Week 16 visit in a 1:1 ratio to receive either risankizumab 150 mg as a single SC injection at Weeks 16, 20, 32, and 44 (Arm 2a) or apremilast 30 mg orally BID up to Week 52 (Arm 2b). Rerandomization will be stratified by PASI 75 response (responder, non-responder) at Week 16. Rescue risankizumab will be offered to subjects who are re-randomized to apremilast (Arm 2b) and are PASI 50 non-responders at Week 28 (Arm 3a; rescue risankizumab will be administered at Weeks 28, 32, and 44) or Week 40 (Arm 3b; rescue risankizumab will be administered at Weeks 40 and 44). The final efficacy evaluation will take place at Week 52.

The schematic of the study is shown in [Figure 1](#). Further details regarding study procedures are located in the Operations Manual ([Appendix F](#)).

Figure 1. Study Schematic

RZB- Risankizumab  
 APR- Apremilast; \*dose titration Day 1 to Day 5  
 \*\*Stratified by PASI 75 Response Status (Yes/No)

↓ Rescue with RZB for APR arm will be offered to subjects < PASI 50 starting at Week 28 **OR** Week 40

BID = twice daily; PASI = Psoriasis Area Severity Index; SC = subcutaneous

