10.2.2 Adverse Event Overview

An overview of AEs will be presented consisting of the number and percentage of subjects experiencing at least one event for each of the following AE categories in each Safety Population:

- Any treatment-emergent AE

- Any treatment-emergent AE related to study drug according to the investigator
- Any severe treatment-emergent AE
- Any serious treatment-emergent AE
- Any treatment-emergent AE leading to discontinuation of study drug
- Any treatment-emergent AE leading to death
- Any treatment-emergent Areas of Safety Interest, as defined in [Appendix B](#).

All deaths will also be summarized:

- Deaths occurring \leq 140 days after last dose of RZB or \leq 28 days after last dose of APR
- Deaths occurring $>$ 140 days after last dose of RZB or $>$ 28 days after last dose of APR

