10.2.3 Treatment-Emergent Adverse Events by SOC and/or PT

The number and percentage of subjects experiencing TEAEs will be tabulated using the Medical Dictionary for Regulatory Activities (MedDRA) system organ class and preferred term, by severity, and by relationship to the study drug as assessed by the investigator. When summarizing the number and percentages of subjects, subjects with multiple occurrences of the same adverse event will be counted once, and only the maximum severity level will be presented in the severity summaries, and the worst/highest relationship level in the relationship summaries.

In addition, treatment-emergent adverse events will be summarized by PT and sorted by decreasing frequency for the risankizumab group.

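### Period B adverse-event windows differ by arm, so the planned subject percentages are not like-for-like; the planned patient-year rates correct most of this, but not all

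*SAP*

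**What the plan says.** SAP 10.2.1 and Protocol 7.5 set the Period B event window by drug. For subjects on risankizumab, events count "Within 140 days after the last dose of RZB in Period B for subjects who receive RZB in Period B". For subjects on apremilast they count "Within the minimum of (i) 28 days after the last dose of APR in Period B and (ii) the first dose date of rescue risankizumab", where rescue was given. Events after rescue have their own definition.

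SAP 10.1 assigns each subject by the first dose received in the period, so a rescued subject stays in the APR/APR group.

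The main displays are by subject. SAP 10.2.2: "An overview of AEs will be presented consisting of the number and percentage of subjects experiencing at least one event". SAP 10.2.3: "The number and percentage of subjects experiencing TEAEs will be tabulated".

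SAP 10.2.4 adds events per 100 patient-years. Its Period B denominators follow the event windows: last dose plus 140 days for the risankizumab arms; last dose plus 28 days, or first rescue dose, for APR/APR. They are capped at end of study and, at the Period B primary analysis, at the data cutoff. Protocol 7.5 asks for both percentages and events per 100 patient-years for SAEs, deaths and discontinuations due to AEs.

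The comparison is a stated aim. Protocol 3.1 says the study will "evaluate the efficacy and safety of switching to risankizumab versus continuing on apremilast" in Week 16 non-responders.

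**The concern.** A percentage of subjects with an event depends on how long each subject is watched. In Period A both arms are cut at the first Period B dose, so continuing subjects have about the same window. Period B has no such cut. The risankizumab tail is longer, and rescue shortens only the apremilast window while the rescued subject stays in the APR/APR denominator. If both drugs carried the same risk, the Period B percentages would still tend to show more affected subjects on risankizumab.

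At stake is how a reader interprets the safety of switching against continuing. The percentage tables are the most visible display, and nothing in the plan says that their Period B columns cover different lengths of time. The plan has no summary restricted to Week 16 to Week 52, the period that both arms share.

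**Working it through.** **Inputs.** Scheduled days (Protocol Appendix D): Week 16 = Day 113, Week 28 = Day 197, Week 40 = Day 281, Week 44 = Day 309, Week 52 = Day 365. Last planned Period B dose (Protocol 4.1): Week 44 for APR/RZB, Week 40 for RZB/RZB, and up to Week 52 for APR/APR. Tails: 140 and 28 days (SAP 10.2.1). The documents give no rescue share, event rate or capture rate after Week 52; those below are assumptions.

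**Check against the plan's own figure.** Protocol 4.1 gives study durations of about 69 weeks (risankizumab) and 61 weeks (apremilast). Screening + last dose + tail: 35/7 + 44 + 140/7 = 69; 35/7 + 52 + 28/7 = 61. Both match.

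**Period B windows.**
- APR/RZB: 309 + 140 − 113 = 336 days
- RZB/RZB: 281 + 140 − 113 = 308 days
- APR/APR, unrescued: 365 + 28 − 113 = 280 days
- APR/APR, rescued at Week 28: 197 − 113 = 84 days
- APR/APR, rescued at Week 40: 281 − 113 = 168 days

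**Effect on percentages when the true risks are equal.** For a rare event the crude risk ratio is close to the ratio of mean windows. For a common event, take a constant hazard with 50% affected in 280 days: p(d) = 1 − 0.5^(d/280). This gives p(336) = 56.5%, p(308) = 53.3%, p(168) = 34.0% and p(84) = 18.8%. Each APR/APR row averages over the assumed rescue shares; for example, 10% and 5% give 0.10×84 + 0.05×168 + 0.85×280 = 254.8 days.

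| Rescued at Week 28 / Week 40 (assumed) | Mean APR/APR days | Rare-event ratio, APR/RZB | Rare-event ratio, RZB/RZB | Common event, APR/APR (APR/RZB is 56.5%) |
|---|---|---|---|---|
| 0% / 0% | 280 | 1.20 | 1.10 | 50.0% |
| 10% / 5% | 254.8 | 1.32 | 1.21 | 46.1% |
| 25% / 10% | 219.8 | 1.53 | 1.40 | 40.6% |
| 50% / 10% | 170.8 | 1.97 | 1.80 | 32.8% |

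The true ratio is 1.00 in every row. The first row needs no rescue assumption.

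**Effect on the planned rates.** Numerator and denominator use the same window, so with a constant equal rate and equal capture the rate ratio is 1.00, with or without rescue. Time after Week 52 has no scheduled site visit, only a safety call. It makes up 84/336 = 25% of the window for APR/RZB, 56/308 = 18% for RZB/RZB and 28/280 = 10% for unrescued APR/APR. If a share c of events in that time is captured, then without rescue, for APR/RZB against APR/APR:
- crude rare-event ratio = (252 + 84c)/(252 + 28c)
- rate ratio = that value × 280/336

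| c (assumed) | Crude ratio | Rate ratio |
|---|---|---|
| 1 | 1.20 | 1.00 |
| 0.5 | 294/266 = 1.11 | 0.92 |
| 0 | 1.00 | 0.83 |

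Poor capture therefore shrinks the error in the percentages and opens one in the rates, in the opposite direction.

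**The case against.** The strongest reply is that the plan already adjusts for exposure. SAP 10.2.4 uses denominators that match the event windows, and Protocol 7.5 pairs percentages with rates for SAEs, deaths and discontinuations. For rare events, counting events or first events makes little difference. The 140- and 28-day tails match the drug-specific AE collection periods in Protocol 6.1, post-rescue events are reported separately, and the safety sections specify no between-arm test. All of this stands. A reader might infer that Period B safety rests on crude percentages alone, or that the plan cannot compare switching with continuing. The documents do not support either reading.

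The windows are also nominal maxima. Under Protocol 5.6 the follow-up call is not required for subjects who start commercial drug at or after Week 52 or the premature discontinuation visit. The cutoff at the Period B primary analysis may leave late enrollees little time after Week 52. Shorter tails bring the no-rescue ratio closer to 1.

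It would also be wrong to set the largest percentage gap beside the lowest rate ratio. The 15.9-point gap at 25%/10% rescue assumes full capture, and the 0.92 rate ratio assumes half. With half capture and no rescue, the common-event figures are 51.7% against 48.2%, a gap of 3.5 points rather than 6.5.

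Three gaps survive. The rates count events (one per preferred term per day), so recurrent events in a few subjects can drive them, and the subject percentages have no exposure-adjusted counterpart. SAP 10.2.4 does not list the categories it covers, and neither document names rates for the safety topics of interest. The rates also include the unequal time after Week 52.

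**Conclusion.** The point holds in a limited form. The Period B subject percentages in SAP 10.2.2 and 10.2.3 are not comparable between arms. With equal constant risk and full follow-up, the rare-event ratio without rescue is about 1.20 for APR/RZB and 1.10 for RZB/RZB. With rescue it is larger: 1.32 to 1.97 for APR/RZB over the assumed shares. These sizes assume that subjects complete dosing on schedule; the rescue shares are illustrations and not forecasts.

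The planned patient-year rates correct most of the problem and are unbiased under a constant rate with equal capture. What they leave is the count of events instead of subjects and the unequal call-only time after Week 52. It would go too far to say that the percentages must show an excess on risankizumab; that follows only under the stated assumptions. This is a worthwhile, inexpensive improvement to the reporting and does not invalidate the safety analysis.

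**What to change.** In SAP 10.2:

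1. State that the Period B between-arm safety comparison rests on exposure-adjusted results.
2. For the overview, SOC/PT, SAE, discontinuation and safety-topic summaries, add subjects with a first event per 100 patient-years at risk. Count from the first Period B dose to the earliest of the Week 52 visit, first rescue dose and end of study. This removes the follow-up asymmetry for subjects who complete dosing and gives the percentages an exposure-adjusted counterpart. State how time is counted after early discontinuation of drug, since Protocol 6.1 collects events for 28 days after apremilast and 140 days after risankizumab.
3. Add a table of subject percentages for Week 16 to Week 28, before any rescue dose. Item 2 is still cut by rescue, rescue depends on PASI 50 non-response, and that censoring may be informative. First-event rates also assume a roughly constant hazard. A window of 84 scheduled days in every arm avoids the rescue cut.
4. Keep the 140/28-day tables, with a footnote that their percentages cover different lengths of time and are not comparable between arms.

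The cost is SAP wording and extra tables from data already collected. Events after Week 52 would then appear only in the follow-up tables, outside the comparative ones. No visit, treatment or existing output changes.
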